To detect a 0.15 difference in the change in the number of overall ED visits between the intervention and comparison groups at a 12 month follow-up, a sample size of 188 will be necessary in the intervention and comparison groups for a total sample size of 376 at the end of 12 months. This number will be sufficient to detect a 0.20 difference in hospitalizations and will also be sufficient to detect differences in cardiac symptoms. In a recent iteration of the intervention, the recruitment response rate was 48% and the loss to follow-up was about 20%. Therefore, 1300 subjects will be contacted for participation and 376 subjects will be enrolled.

Analysis of patient outcomes:

Descriptive statistics will be computed for all outcomes overall and stratified by randomized study arms. Health care utilization: Outcome variables including hospitalizations and ED visits will first be assessed as dichotomous variables and will be analyzed using chi-square analyses followed by logistic regression modeling. Because these are count variables, Poisson regression analyses will also be conducted. Cardiac symptoms: The presence of cardiac symptoms will be assessed individually using chi square tests and logistic regression modeling. The cardiac symptoms will also be summed to obtain an overall score of symptoms as well as a score for the frequency and severity. These will be continuous and will be analyzed using analysis of covariance (ANCOVA) and multiple linear-regression modeling assuming normal distributions. If necessary, transformation will be used to ensure normality or Poisson regression will be used if Poisson distributions are found for these variables. They may also be recoded as categorical or ordinal variables and analyzed using chi-square tests and multiple or cumulative logistic regressions.

Functional health status: Functional health status will be assessed using the PROMIS Global Health Scale and/or PROMIS-29. The scores are continuous variables and will be analyzed similarly to the symptoms using ANCOVA and linear regression modeling where the normality assumption is appropriate. They may also be re-coded as categorical or ordinal variables and analyzed using chi-square tests and logistic regressions.

Intervention dose received: The dose of the intervention will be examined using the logs completed by the health educator. The subject will receive one point for each of 4 sessions attended and a point for each of the three components completed: goal setting, tracking form, and the judgment/reaction. The scores will only be available for the intervention group and will describe average level of participation within the intervention group using frequencies and mean scores.

The components of the intervention: Observation, judgment, goal setting strategies, outcome expectancy and efficacy can also be described individually. Participants in the intervention group may be stratified based on the dose score and outcomes compared using t-tests or chi-square tests of homogeneity to describe impact of dose on outcomes. Instrumental variable approaches to estimating the complier-average causal effect of the intervention will be applied, with compliance defined using two different choices of cut-off on the performance score.

Change over time: The focus of the mixed-model (for continuous outcomes) and GEE (for discrete outcomes) analyses will be to assess changes in dependent measures over time, and whether these changes differ between program participants and "usual care" controls. The effect of time as well as the interaction between time and program participation (program vs. waitlist control) will be included as factors in all models.

Generalizability of the intervention: To determine how effective the intervention would be if duplicated in a similar population, it will be important to examine non-consenters to see if those who choose to participate have certain factors that may be correlated with improved outcomes not present in those who do not participate. Aggregate data from the DMC including demographics, and health care use values will be obtained on those patients that meet the criteria for participation but were not enrolled in the randomized controlled trial to be compared to enrolled participants using t-tests and chi-square tests to discover any differences.

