Throughout recruitment calls, each patient will be encouraged to ask questions and told that they are free to withdraw from the study at any time, for any reason. A toll-free [contact]) will be provided so that potential participants can call the research office with additional questions at any time.

Randomization will be stratified by four categories of a risk score based on data from prior studies that includes age, gender, and number of comorbidities, using responses from the baseline interview. To reduce the predictability and resulting bias due to block randomization, random block sizes (e.g., lengths of 8, 10, 12 subjects) will be used and blinded to investigators. Prior to recruitment, a permuted block randomization schedule will be created using the RANTBL and RANUNI functions in SAS to generate blocks with varying sizes of 8, 10, or 12 and random numbers for group assignment within each of the 4 categories of risk score.

Once enrolled, participants recruited through the Detroit Medical Center (DMC), will be asked to complete another consent document that includes a HIPAA Authorization statement. This will authorize DMC to release specific health information related to Take Heart after the recruitment phase (first, middle and last name, street address, city, state, zip code, email address, home and cell phone number, primary care provider and specialist, number of visits to the emergency department and hospitalizations during the year prior to the Take Heart study and the year of your participation in the study), to the University of Michigan School of Public Health research staff.

WHAT HAPPENS TO SUBJECTS DURING RESEARCH:

Focus groups:

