Participants assigned to the Take Heart Program Group will be asked to talk to a health educator/heart disease counselor 2 times over the phone, and 5 times in person as part of a group. Health educators will be trained DAAA staff members, and will have background/experience in health promotion, health education, health coaching, or related areas but will not necessarily have clinical training. There are 7 total combined phone and group education sessions over a total of 7 weeks during which they will learn ways to manage heart disease. More information about the program content and process is found in the Study Background document. Each telephone session will be 30-50 minutes, and each group session will last 120-180 minutes. Telephone sessions will be audio recorded for guality assurance purposes. Participants will also be provided a binder of materials as part of this program. After completing the 7 weeks of groups and phone sessions, the health educator will check in with each participant 3 more times throughout the course of the year, at the 3, 6 and 9-month marks. Two of these check ins will be via mail (3 months and 9 months); each participant will receive a Take Heart newsletter tailored to the main topic of their goals. The 6-month check in will be via phone; the health educator will call each participant to follow up with them, check in on their goals and answer any questions they may have at that time. This phone call will also be audio recorded. These check-ins are intended to help keep participants motivated to continue working on their goals and remind them of their participation in the Take Heart program. Individuals in the waitlist/control group will receive usual care. If time and funding allows they will have the opportunity to participate in the Take Heart intervention once they have completed their followup (12-month) survey.

DATA COLLECTION:

Pilot Study

Data sources for the pilot study include: (1) CMCD observer notes from the education sessions; (2) qualitative data gathered through the participant debrief; and (4) quantitative and qualitative data gathered from the pilot-test of the baseline questionnaire.

Observer notes: at each education session a member of the CMCD research will be present taking notes about session activities and participant response.

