Intervention fidelity will be assessed at two levels. The first level will compare the adapted with the original program. A second level of fidelity assessment, employed in previous work by the CMCD, will examine how the adapted program is implemented by DAAA. Those charged with delivering the adapted program may not maintain full fidelity or protocols may need to change mid-stream in response to unanticipated issues. The CMCD will assess fidelity in partnership with DAAA and RPC personnel. At the end of each session, the health educator will fill out a "fidelity checklist', summarizing delivery of the core components of the program: teaching the "PRIDE" problem solving process, number of sessions attended, observation tools distribution, and an interactive discussion format. CMCD staff will observe a randomly-selected subset of "take PRIDE" sessions to assess coverage of core components and other key intervention processes, using a standardized rating form. The proposed study team has employed fidelity tools and logs for clinical trials that have informed the development of these draft tools; they will be further refined for this project and tested during the pilot-study in Aim 1. A qualitative and contextual approach to fidelity will be employed through a systematic ongoing process assessment. This will include annual in-depth interviews with key stakeholders (staff). These interviews will explore and document the barriers and facilitating factors experienced in terms of program implementation, as per Specific Aim 3 of the study - ""Assess the process of translation and implementation of the intervention in the target setting and identify factors that help or hinder the process." Interview protocols for staff will be developed to explore perspective and meaning about implementation; (e.g., reasons for adaptation). These protocols will be based on those developed for previous CMCD dissemination projects but will be refined for the current project.

DATA STORAGE:

Focus groups:

The following steps will ensure that participants' privacy will be maintained:

1) No names or other identifying information will be included in the transcribed focus group discussions, and thus no information will be included in any published or unpublished reports using interview data that could be used to identify any participant.

2) Participants' names will not be included on the short supplemental written survey; these will be anonymous.

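### Only the intervention arm is taught in groups, and the plan states no allowance for correlation within a class, either behind the 188 per arm or in the listed analyses.

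*Combined protocol and SAP*

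**What the plan says.** **Randomization** (main-study part of the screening, consent and enrollment section). Individuals are allocated: "Randomization will be stratified by four categories of a risk score based on data from prior studies", using permuted blocks.

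**Delivery** (What Happens to Subjects During Research, Main Study). The program arm is seen "2 times over the phone, and 5 times in person as part of a group". Each group session lasts 120-180 minutes. On the other side, "Individuals in the waitlist/control group will receive usual care", with the program offered only after the 12-month survey and only if resources permit. The fidelity paragraph under Data Collection counts "observation tools distribution, and an interactive discussion format" among the core components, so exchange between classmates is part of the treatment.

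**Sample size** (Sample Size Determination). For a 0.15 difference in the change in overall ED visits, "a sample size of 188 will be necessary in the intervention and comparison groups". In a recent iteration of the intervention, "the loss to follow-up was about 20" percent. No alpha, power, standard deviation, class size, ICC or design effect is given.

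**Analysis** (Analysis of patient outcomes). Hospitalizations and ED visits "will first be assessed as dichotomous variables and will be analyzed using chi-square analyses followed by logistic regression modeling", with Poisson regression added. Symptom scores go to ANCOVA and linear regression. The mixed models and GEE in the Change over time paragraph concern repeated measures; the terms named are "The effect of time as well as the interaction between time and program participation". No class or educator term appears.

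Main-study class size, the number of educators and whether class membership is fixed are not stated.

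**The concern.** This is a partially nested design: program patients share classmates, an educator and discussion, while controls are ungrouped. Correlation created by that sharing arises after randomization, so randomizing individuals does not remove it. The variance of the program-arm mean would then exceed what a patient-level model assumes. Confidence intervals would be too narrow, the 5% test would reject too often, and true power would be below its value under independence. The primary outcomes, ED visits and hospitalizations, would be affected. A GEE or mixed model that clusters on the patient for two time points does not address correlation between patients in the same class.

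The source of the similarity matters. If classmates resemble each other only because they were scheduled together, for example by neighbourhood, the same mix is present in both arms by randomization and the patient-level test keeps its level.

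**Working it through.** **1. The plan's own figure.** For two means, n per arm = 2 × SD² × (z_α + z_β)² / δ². The plan gives δ = 0.15 and n = 188 but no alpha, power or SD, so 188 cannot be reproduced. Under an assumed two-sided 5% test with 80% power, the implied SD is 0.15 × √(188/2) / 2.802 = 0.519; with 90% power it is 0.449. Obtaining 188 from these SDs is circular. The SD cancels from everything below.

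**2. Inputs assumed, not in the documents.**
- ICC from delivery: 0.01-0.05.
- Class size: the only guide is the pilot, 20 patients in one or two series, hence 10-20 scheduled. Applying the plan's 20% loss gives m = 8-16 analysed per class. The pilot format differs, and another pilot paragraph speaks of two series, which favours the lower end.
- Two-sided 5% test; 80% power at 188 per arm under independence.

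**3. Formulas.** Design effect in the program arm DE = 1 + (m − 1) × ICC, and 1 in controls. Variance inflation of the difference VIF = (1 + DE)/2. Type I error of the patient-level test = 2 × [1 − Φ(1.96/√VIF)]. Power with the correct variance = Φ(2.802/√VIF − 1.96). Detectable difference at 80% power = 0.15 × √VIF.

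**4. Results at 188 per arm, clustering alone.**

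| m | ICC | DE | VIF | Type I | Power | Detectable |
|---|---|---|---|---|---|---|
| 8 | 0.01 | 1.07 | 1.035 | 5.4% | 78.6% | 0.153 |
| 8 | 0.05 | 1.35 | 1.175 | 7.1% | 73.4% | 0.163 |
| 16 | 0.01 | 1.15 | 1.075 | 5.9% | 77.1% | 0.156 |
| 16 | 0.05 | 1.75 | 1.375 | 9.5% | 66.6% | 0.176 |

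From an assumed 90% start, replacing 2.802 by 3.242, power is 89.0-84.9% (m = 8) and 87.8-78.9% (m = 16).

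**5. At the number likely to be analysed.** If 376 are enrolled and 20% are lost, 376 × 0.8 ≈ 300 remain, about 150 per arm. Attrition alone moves the detectable difference to 0.15 × √(188/150) = 0.168 and the assumed 80% power to 70.6%. Multiplying 0.168 by √VIF gives 0.171-0.182 (m = 8) and 0.174-0.197 (m = 16).

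**6. Simulation check.** Continuous outcome, 20,000 replicates, 150 analysed per arm, correlation created by delivery: patient-level type I error at ICC 0.01 and 0.05 was 5.4% and 7.0% with 19 classes, and 5.9% and 9.8% with 9 classes, in line with the formula. With 188 per arm:
- At ICC 0, a class-clustered test had power 79.0% (18 classes) and 77.2% (9 classes), against about 80% at patient level.
- With sorting only, the patient-level test stayed at 4.9-5.1%. The class-clustered test was conservative: 4.5-3.0% (18 classes) and 4.2-2.0% (9 classes) at ICC 0.01-0.05.
- For assumed binary and count outcomes at ICC 0-0.05, class-clustered type I error was 4.7-5.6% with a small-sample correction and 5.5-7.9% without.
- With correlation from two educators only, the class-clustered test rejected 9.4-10.1% of the time at ICC 0.01 and 22.5-25.4% at 0.05.

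**The case against.** The strongest reply is that nothing in the documents shows that delivery creates any correlation. The primary outcomes are utilization counts assessed at 12 months, well after a 7-week program. Half of the ten planned program contacts are individual: two phone sessions, one check-in call and two mailed newsletters, against five group sessions. With an ICC near zero the planned analysis is right and a class-adjusted one only loses power. This stands, and it is why the point is conditional.

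A second reply is that the derivation of 188 is not shown and the GEE and mixed-model cluster structure is not fully described, so an unstated allowance cannot be excluded. That stands too: the finding is that none is stated.

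A third is that a class-aware test has faults of its own: it is conservative under sorting and unprotected against educator effects when educators are few. This argues for a sensitivity analysis, not a replacement.

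A reader might infer that 188 is too small and must be inflated, or that the planned tests are invalid. The documents support neither. Both need an ICC and a class size that the plan does not give, and attrition on its own would take more power than clustering does in three of the four cases tabulated above.

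**Conclusion.** The point holds in conditional form. One arm is grouped, interaction is part of the treatment, and no allowance for class is stated in the sample size or the analyses. If delivery induces an ICC of 0.01-0.05 with 8-16 analysed per class, the nominal 5% test runs at 5.4-9.5%, and an assumed 80% power at 188 per arm becomes 79-67%. The upper figures need both the larger class and the higher ICC; the lower ones are negligible. All of these inputs are assumptions, and the calculation takes equal class sizes and a normal approximation. Within-class similarity by itself would not show that the patient-level test is wrong, because an observed ICC mixes sorting with delivery. The change is worth making because it is cheap and because choosing between standard errors after seeing the data would be hard to defend.

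**What to change.** 1. Record the scheduled class ID and educator ID for every program patient. The Detroit Area Agency on Aging already schedules sessions and collects attendance, and educators keep logs, so this is a check or one or two added fields.
2. Pre-specify one class-aware sensitivity analysis of ED visits and hospitalizations: class-clustered standard errors, each control as a singleton, and a small-sample correction. Keep patients in their first scheduled class whether or not they attend or switch. For continuous secondary outcomes, use a random class effect in the program arm only. State in advance that the patient-level analysis stays primary, and that a conclusion which changes under the class-aware analysis will be reported as not robust to clustering.
3. Report the number of classes and educators and the estimated ICC, noting that it cannot separate sorting from delivery and that class clustering does not capture educator correlation when educators are few.
4. Give the detectable difference over an assumed ICC range at the number expected to be analysed, without enrolling more patients.

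Cost: SAP text, some code and possibly the log fields. The sensitivity analysis will have somewhat wider intervals, loses about 1-2.5 power points if the ICC is 0, and is conservative if the correlation is only sorting.

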Data management will be responsible for monitoring interviews completed, which will be done monthly. The interviewers will be sent a list of interviews that have not yet been completed with study participants. This process differs from query letters which request information on specific data items within a form.

Data management will periodically conduct an audit program. A random subset of cases will be selected from the files. In this way, problems with data collection and transmission can be detected early. In addition, data will be monitored for secular trends in data completeness and quality. Study audits will be conducted several times over the course of the study.

Only the study generated ID will used for any and all references to records for purposes of cleaning and overall quality.

***Ame00068213

We added the University of Michigan IRB to the language about the HIPAA waiver for recruitment and language about the HIPAA authorization for enrolled participants recruited from the Detroit Medical Center.

Study Statistical Design

Sample Size Determination:

The primary outcomes of interest in the randomized trial are ED visits and hospitalizations, both overall and heart related. In a sample of 443 patients at a 12 month follow-up, there were significant differences between those that received "take PRIDE" and those that did not in hospitalizations overall (difference of 0.26 times hospitalized) and heart related hospitalizations (difference of 0.41 times hospitalized) and also in overall ED visits (difference of 0.17 visits). The secondary outcome of interest is cardiac symptom experience: number, frequency, and bothersomeness. Several cardiac symptoms will be summed to obtain overall scores: chest pain, shortness of breath, waking with chest pain, waking with shortness of breath, and palpitations. In a sample of 460 patients randomized to the intervention or usual care, researchers found that the change in the number and frequency of symptoms differed significantly between the intervention and comparison group (difference of 0.36 and 1.16 in scores, respectively).

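### Four unranked primary outcomes, tested both as any/none and as counts, with no deciding outcome, decisive test, significance level or multiplicity rule

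*Combined protocol and SAP*

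**What the plan says.** Under Study Statistical Design, Sample Size Determination, the combined protocol and SAP states: "The primary outcomes of interest in the randomized trial are ED visits and hospitalizations, both overall and heart related". That makes four outcomes. They are set apart from the next tier ("The secondary outcome of interest is cardiac symptom experience: number, frequency, and bothersomeness") but not ordered among themselves.

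The same section derives 188 per arm, 376 in total at 12 months, as follows: "To detect a 0.15 difference in the change in the number of overall ED visits between the intervention and comparison groups". It then adds: "This number will be sufficient to detect a 0.20 difference in hospitalizations". It does not say whether these are overall or heart-related hospitalizations.

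Under Analysis of patient outcomes, hospitalizations and ED visits "will first be assessed as dichotomous variables and will be analyzed using chi-square analyses followed by logistic regression modeling". The next sentence reads: "Because these are count variables, Poisson regression analyses will also be conducted". The heart-related versions are not listed separately there; presumably they are included.

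The Change over time paragraph adds a further route, "GEE (for discrete outcomes) analyses will be to assess changes in dependent measures over time", and says that "the interaction between time and program participation (program vs. waitlist control) will be included as factors in all models". It gives neither the link function nor the variance estimator.

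No section states a significance level, sidedness, whether one or all primary outcomes must succeed, or how multiple tests are handled.

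**The concern.** A reader of the final results could not tell from the plan which finding decides the trial. Mixed results are realistic. Sample Size Determination reports significant earlier differences for overall hospitalizations (0.26), heart-related hospitalizations (0.41) and overall ED visits (0.17), and reports none for heart-related ED visits. The any/none and count analyses of the same outcome can also disagree, and no rule says which prevails.

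If a favourable result on any one outcome, by either method, could be presented as success, the chance of declaring benefit from an ineffective program would exceed the nominal level.

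**Working it through.** **1. The plan's own figure.** Stated inputs: 188 per arm and a 0.15 difference in change. Not stated: SD, alpha, sidedness and power. The figure therefore cannot be reproduced, only solved backwards. With two-sided 5% and 80% power (both assumed):

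SD = 0.15 × √(188/2) / (1.960 + 0.842) = 0.519.

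At 90% power the implied SD is 0.449. Neither is shown to be wrong; they cannot be checked.

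**2. Independent tests.** With two-sided 5% per test (assumed) and any one of four counting as success: 1 − 0.95⁴ = 0.185.

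**3. Correlated tests.** The four outcomes overlap, so independence is only a guide. A null simulation used 188 per arm and 40 scenarios of 6,000 trials each (Monte Carlo SE about 0.003 at 5% and 0.005 at 17%). The documents supply none of the following, so all are assumptions:
- mean ED visits of 0.135, 0.5 or 1.0 per year, and hospitalizations of 0.135-0.9;
- heart-related share of 0.4 or 0.9, nested in overall;
- 0-95% of hospitalizations arising from an ED visit;
- gamma frailty variance of 0.5 or 1.5, shared across outcomes and both years.

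| Method | P(at least one of four p<0.05) |
|---|---|
| Chi-square only | 0.082-0.174 |
| Robust 12-month count only | 0.078-0.167 |
| Log-link GEE, time-by-program, only | 0.084-0.178 |
| Baseline-adjusted robust count only | 0.080-0.175 |
| Chi-square or robust count, ED rate 0.5 or 1.0 | 0.138-0.247 |
| Chi-square or robust count, ED rate 0.135 | 0.107-0.205 |

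One valid method per outcome thus gives about 8-18%, and either of two methods about 11-25%. A separate simulation (20,000 trials in each of four scenarios, ED rates 0.5-1.0) gave 0.127-0.163 with one method and 0.192-0.223 with either.

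The robust count test stands in for the plan's Poisson model. Plain Poisson on overall ED visits alone rejected in 0.050-0.222 of null trials. That is overdispersion, a separate problem, and is kept out of the table.

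**4. With one outcome and one test.** Overall ED visits alone: 0.044-0.058 (GEE) or 0.044-0.056 (baseline-adjusted). Holm among the other three, even if the gate always opened: 0.024-0.054.

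**5. Power under each error rule.**
- *Holm across four.* The first step is at 0.05/4 = 0.0125, critical value 2.498. A test with 80% power at 5% has a standardised effect of 2.802, so power is Φ(2.802 − 2.498) = 0.62 in the worst case.
- *Gate on overall ED visits.* In the assumed frailty model the SD of change is √(2 × mean): 1.0 at 0.5 visits per year and 1.414 at 1.0. For a difference of 0.15, power is about Φ(0.15 / (SD × √(2/188)) − 1.96), or 0.31 and 0.18. Simulated power is 0.39 and 0.20 with the log-link GEE, and 0.48-0.54 and 0.23-0.27 with a baseline-adjusted count model.

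**The case against.** The best reply is that the plan does have a lead. The sample size is keyed to the difference in change in overall ED visits, and the Change over time analysis asks whether changes differ between arms, with the time-by-program term in all models. Outcome and model line up, and a sympathetic reader could take them as the primary analysis. This stands as an implicit lead only. The plan does not call that outcome deciding, and the same paragraph also claims adequacy for hospitalizations and cardiac symptoms. The analysis listed first is any/none, not the change in count. Saying that it comes first gives an order of work, not a decisive test.

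It is also fair that the simulated ranges are mostly assumption. That stands, but the missing rule does not depend on them.

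Three stronger readings go beyond the documents:
- A reader might infer that the trial's error rate is 18.5% or more. That requires an any-one-wins rule and 5% per test, neither of which is stated. The low end with one method is about 8%.
- A reader might infer that the plan expressly analyses all four outcomes both ways. For the heart-related versions this is an inference.
- A reader might equate the implied SD of 0.519 with √(2 × mean) and take 0.135 visits per year as the rate at which the planned N gives 80% power. It cannot be: 0.135 − 0.15 is negative. With treated follow-up visits reduced by 0.15, the variances of change in the two arms sum to 4 × mean − 0.15 + 0.0225 × frailty variance. Setting this to 2 × 0.519² gives a mean of about 0.16-0.17. The 0.135 case is only an arbitrary low-rate scenario.

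**Conclusion.** The concern holds. The plan names four unranked primary outcomes and commits to more than one analysis of ED visits and hospitalizations. It supplies no deciding outcome, decisive test, significance level or multiplicity rule. That omission can be read directly from the text and needs no assumption.

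Its size is conditional. It rests on two-sided 5% per test, on success on any one outcome counting, and, for the simulated ranges of about 8-18% and 11-25%, on assumed event rates and correlations.

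The trial can run as planned, but its primary conclusion could not be read unambiguously. The gap should be closed before analysis.

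**What to change.** Before analysis, state the following in the SAP:

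1. **One decisive analysis for all four outcomes, on the count scale used for sizing.** This is a single pre-stated count model that accounts for baseline and has robust variance: either the time-by-program GEE already planned or a baseline-adjusted count model. State the link and the effect scale. A log-link interaction tests a ratio of rate ratios, whereas the 0.15 used for sizing is an absolute difference in change.
2. **The utilization data source.** Roles/Responsibilities describes extraction from Detroit Medical Center records for consenting participants, while Data Collection (Main Study) lists only telephone surveys and educator logs. Unless one source is named, a single outcome could still yield two results.
3. **A rule holding overall error at two-sided 5%, chosen by the sponsor.** Either Holm across the four outcomes, or overall ED visits as the single primary with the other three tested only if it succeeds (fixed order or Holm).
4. **The any/none and remaining analyses labelled supportive.**

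The change is wording only, with the same data and N. The cost is power per outcome. Under Holm, a test with 80% power at 5% falls to about 62% in the worst case. Under the gate, the other three outcomes are confirmatory only if ED visits succeed, with assumed power of about 18-54% for a 0.15 difference at 0.5-1.0 visits per year. The gate is also debatable because the earlier differences were larger for hospitalizations than for ED visits. The documents give no SD, so actual power cannot be stated.
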